## 6. Study Participants

### 6.1. Study Population

Participants will be recruited through the Prolific panel. Participants must meet both criteria for eligibility: (1) be at least 21 years old; (2) have consumed more than three alcoholic drinks per week over the past year, which is to ensure they are current moderate or heavy drinkers defined by the Centers for Disease Control and Prevention (2018); and (3) be willing to participate in remote eye tracking tasks and have necessary technical support to complete remote eye tracking tasks (i.e., having access to high-speed Internet and a computer/tablet/phone equipped with a high-speed camera). We will carry out the initial screening over an online survey.

### 6.2. Number of Participants

Number of people expected to be screened: 3,000

Number of people expected to be enrolled: 800.

#### 6.2.1. Sample Size

No previously published work has examined the effect of narrative (vs. non-narrative) PWLs on visual attention and reactance. In our preliminary work, we conducted an online experiment testing the effect of PWLs type among adult moderate and heavy drinkers. We found that participants who saw non-narrative PWLs reported significantly higher reactance to the warnings than those who saw narrative PWLs ( $r = .19$ ).

Therefore, in the proposed project, we will use the effect size of  $r = .19$  to estimate the sample size. With the alpha level set at .05, we will need 213 participants to achieve a statistical power of .80. The final sample size needs to account for possible failure to (1) complete the eye-tracking task and (2) generate usable eye-tracking data for those who complete the task. Based on a recent remote eye-tracking study (Chen-Sankey et al., 2023) and information provided by the Sticky by Tobii team, we plan to screen 1,200 participants (41% rate of completion) and enroll 500 participants (43% rate of usable data).

Because risk perceptions and behavior intentions are also our primary outcomes, we conducted an additional power analysis to calculate the sample size for these two

outcomes. Based on previous research (e.g., Oschatz & Marker, 2020), narratives had a small effect on persuasion. With the alpha level set at .05, we would need at least 800 participants to detect an effect of  $d = .20$  with 80% power in an independent t-test.

Given that the sample size to detect a significant effect on risk perceptions and behavior intentions ( $N=800$ ) is larger than that on reactance ( $N=500$ ), we decided to enroll 800 participants in our main experiment. Accordingly, we would need to screen 1,951 participants (41% rate of completion).

Running the study resulted in 1,045 eligible participants from 1,922 screened participants. Of the 1,045 eligible participants, only 404 participants so far completed the main experiment successfully. Increasing the screener eligibility to 3,000 is expected to increase the successful completion of the main study to the projected 800.

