## 6.9. Withdrawal/Termination

Participants can choose to stop their participation at any time. Because this research project consists of three parts: the screening survey, the main experiment, and the follow-up survey. In the event participants withdrawal after completing one part, their data for the completed part will be kept. For example, a participant completes the main experiment but not the follow-up survey, their data in the main experiment will be kept.

Note that Sticky by Tobii (the webcam-based eye-tracking) will report a "terminated" category from those that begin the eye-tracking portion of the study. These include participants that terminate their participation voluntarily (e.g., close the browser) and encounter technical failures (e.g., cannot calibrate). If a participant is terminated by the eye-tracking platform, they will not be allowed to complete the rest of the study because

the remaining questions depend on the stimuli embedded in the eye-tracking task. Thus, the terminated participants will be requested to return their submissions. In this case, their data will be removed. Given that participants will answer a few questions before they are directed to the webcam-based eye-tracking platform, partial payments will be made to those who encounter technical failures but not those who withdraw from the study.

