### **11.2. Protocol Deviations**

A potential protocol deviation is related to the sample size. As mentioned, we plan to screen 1,200 participants and enroll 500 participants for the main study. If we do not have 500 eligible participants signed up for the main study after screening 1,200 participants, we will need to continue the screening study. Similarly, if we do not have 213 completed participants to achieve a statistical power of .80, we will also need to continue the screening study and enroll more participants in the main experiment. In addition, if participant demographic distribution does not approximate the demographics of the general population in the United States (e.g., not enough racial minority participants), we will recruit participants from the specific populations on Prolific for the screening survey and the main study until the sample approximates the U.S. demographics. We will report the protocol deviations to the BRANY IRB following their policies and procedures.

Another potential deviation is related to the experiment stimuli. The stylistic design of the PWLs may be changed, such as adding a border to each PWL or using a black background and white text (the current version uses a white background and black text). However, the content of the image and text will remain the same.

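### The reported counts project about 631 completers from 3,000 screened, not 800, and no continue-screening trigger in 11.2 is tied to 800

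*Combined protocol and SAP*

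**What the plan says.** Section 6.2.1 gives two sample-size arguments. The first uses r = .19 for reactance, needs 213 participants, and leads to 1,200 screened and 500 enrolled. The second covers risk perceptions and intentions: "we would need at least 800 participants to detect an effect of" d = .20 with 80% power. The larger number governs, and the section concludes that "we would need to screen 1,951 participants (41% rate of completion").

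It then reports progress. "Running the study resulted in 1,045 eligible participants from 1,922 screened participants", and of those eligible "only 404 participants so far completed the main experiment successfully". The response is to screen more: "Increasing the screener eligibility to 3,000 is expected to increase the successful completion of the main study to the projected 800". Section 6.2 makes clear what the 3,000 counts: "Number of people expected to be screened: 3,000".

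Section 6.9 fixes who can contribute to the later outcomes: "If a participant is terminated by the eye-tracking platform, they will not be allowed to complete the rest of the study". The data of those participants are removed. Completers are therefore the sample for risk perceptions and intentions.

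Section 11.2 sets out when recruitment would continue. It still uses 1,200 screened and 500 signed up, and adds: "if we do not have 213 completed participants to achieve a statistical power of .80, we will also need to continue the screening study". It also has a demographic trigger without a number. It does not mention 800, 1,951 or 3,000.

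**The concern.** The projection of 800 stands beside the counts that should support it, and the two disagree. The first 1,922 people screened gave 404 completers. Another 1,078 would have to give almost as many again (396), and the plan offers no reason for the yield to rise.

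At stake is the power for H2. Risk perceptions and intentions are primary outcomes, and 800 is the number to which the plan attaches 80% power. If the study closed at 3,000 screened with an unchanged yield, a null H2 result would be harder to interpret than the plan implies. Section 11.2 would not catch this, because none of its numeric triggers refers to 800 completers. Randomisation, outcome definitions and the analysis methods are not affected.

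**Working it through.** **Inputs.** From 6.2.1: 1,922 screened, 1,045 eligible, 404 completed so far, a 41% completion rate, d = .20, alpha .05, power 80%, N = 800. From 6.2: 3,000 screened. Sidedness and allocation ratio are not stated; two-sided and 1:1 are assumed.

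**The plan's own figures.** A two-sided t-test for d = .20 at 80% power needs 787 in total (noncentral t), or 788 with equal arms. Power at 800 is 80.6%. The stated 800 therefore reproduces. A one-sided test would need only 620, which supports the two-sided reading. The planned screening number also reproduces: 800/0.41 = 1,951.

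**Rates so far.**
- Eligible among screened: 1,045/1,922 = 54.4%
- Completed among eligible: 404/1,045 = 38.7%
- Completed among screened: 404/1,922 = 21.0%

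**Projection at constant yield.** 3,000 × 404/1,922 = 630.6, about 631. The variance for the remaining 1,078 screened is 1,078 × 0.2102 × 0.7898 = 179 from binomial variation, plus 1,078² × 0.2102 × 0.7898/1,922 = 100 from uncertainty in the rate. The SD is √279 = 16.7, so the approximate 95% prediction interval is 631 ± 33, or 598 to 663.

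**Power for d = .20.** At N = 631, power is 70.8%; across 598 to 663 it runs from about 68% to 73%. At N = 631, 80% power applies to d = 0.223.

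**Where the gap comes from.** The 1,951 applies 41% directly to people screened: 41% of 1,922 is 788, against 404 observed. Completion among eligible people is 38.7% (95% interval about 36% to 42%), which is consistent with 41%. The step left out is eligibility. Putting it in does not recover 800: 3,000 × 0.5437 = 1,631 expected eligible, and 41% of 1,631 is 669.

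**What 800 from 3,000 would require.**
- With no late completers: 800 − 404 = 396 from 1,078 newly screened. That is 36.7% of screened, or 67.6% of their expected 586 eligible (1,078 × 0.5437).
- With late completers among the 1,045 − 404 = 641 eligible non-completers, and new eligible people reaching the same raised eventual rate: 800 × 1,922/3,000 = 512.5, less 404, is about 109 (17% of 641).
- With late completers, but newly screened people still yielding 21.0% (about 227): 800 − 631 = 169 (26% of 641). Under this assumption 109 late completers would give 404 + 109 + 227 = 740, with about 78% power.

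**Screening needed at the observed yield.** 800/0.2102 = 3,806, about 3,810.

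**The 11.2 triggers.** The 1,922 screened and 404 completers already exceed 1,200 and 213. If 213 means participants with usable eye-tracking data at the planned 43%, 404 × 0.43 = 174 is still short of it, but 631 × 0.43 = 271 is not. On either reading, 213 would not hold screening open beyond 631 completers.

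**The case against.** The strongest reply is that nothing has yet gone wrong. The 404 is a count to date, so some of the 641 eligible non-completers may still finish. The 3,000 is an expected number, not a limit. When screening near the planned 1,951 fell short, the response was to extend it towards 800, and 11.2 lists potential deviations and is not a stopping rule. All of this stands, and it makes the power loss conditional. It does not supply the missing support for 800: the documents do not say how many invitations are open or what late completion is expected.

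Two stronger readings are tempting. A reader might infer that the study's data refute the 41% rate. They refute it as a rate per person screened, which is how 1,951 used it, but not as a rate per eligible person. A reader might also infer that every number in 11.2 is obsolete, including 213. Section 6.2.1 replaces only the screening and enrolment targets; 213 remains its stated requirement for the r = .19 analysis behind H1. Deleting it would remove the only numeric trigger tied to H1 power.

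It is also fair to say that the worst case is moderate: the effect detectable with 80% power moves from d = .20 to about 0.22.

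**Conclusion.** The projection of 800 completers from 3,000 screened is not supported by the counts printed with it. At constant yield the figure is about 631 (598 to 663), with about 71% power for d = .20 under a two-sided test with 1:1 allocation. The arithmetic is firm. The consequence holds only if screening stops at 3,000 and the yield does not rise, and the documents state neither. They do not support the claim that the trial will be underpowered. They do support the narrower claim that the plan gives no basis for 800 and that 11.2 has no trigger that would protect it. This should be fixed while recruitment is open; it does not threaten the validity of the design.

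**What to change.** In 6.2 and 6.2.1, do one of the following:

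- (a) Restate the projection as about 630 completers, with about 71% power for d = .20 and 80% power for d of about 0.22.
- (b) Keep 800 from 3,000 screened and state the late-completion assumption behind it: about 109 of the 641 (17%) if new eligible people reach the same eventual rate, or about 169 (26%) if newly screened people yield 21.0%. Say how many invitations are still open.
- (c) Keep 800 and restate the expected number screened as about 3,810 at the observed yield.

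In 11.2, update the 1,200 screened and 500 enrolled targets, and keep 213 as the H1 requirement. If 800 is kept, add a continue-screening trigger at 800 completers. In 6.2.1, replace the term *screener eligibility* with *number screened*, because the 3,000 could otherwise be taken as eligible people.

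**Cost.** Options (a) and (b) and the 11.2 changes are wording only, though (a) states a less favourable power. Option (c) lengthens recruitment. At the 6.8 payment rates plus the 25% fee it costs at most:
- 806 more screeners × $0.20 × 1.25 = about $201
- up to 269 partial payments (806 × 0.5437 × 0.613) × $0.20 × 1.25 = about $67
- 169 more completers × $3 × 1.25 = about $634
- up to 169 follow-up surveys × $1 × 1.25 = about $211

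The total is about $1,113. The documents show no total budget, so whether payments for 800 completers are already funded is unknown.

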### **6.3. Eligibility**

Inclusion criteria: (1) be at least 21 years old; (2) have consumed more than three alcoholic drinks per week over the past year; and (3) be willing to participate in remote eye tracking tasks and have necessary technical support to complete remote eye tracking tasks (i.e., having access to high-speed Internet and a computer/tablet/phone equipped with a high-speed camera).

Exclusion criteria: (1) be younger than 21 years old; (2) has not consumed more than three alcoholic drinks per week over the past year; and (3) be not willing to participate in remote eye tracking tasks and have necessary technical support to complete remote eye tracking tasks (i.e., having access to high-speed Internet and a computer/tablet/phone equipped with a high-speed camera).

We will use a short online screening survey to determine eligibility. A copy of the screening survey is included in the submission. The screening data will not be retained about individuals who are not enrolled in the research. The screening data will only include their Prolific ID, but not other types of identifiers.

### **6.4. Vulnerable Populations**

This study will not enroll vulnerable populations.

## 6.6. Consent/Accent Procedures

After eligible participants sign up for the study, they will be provided with a link to the online experiment. At the beginning of the study, participants will be asked to read the consent form and click the 'I accept' button to proceed. To ensure participants can understand the consent, the information will be written at no higher than an eighth-grade reading level. Participants will also be informed that their decision to participate in this study is voluntary. They can choose to stop their participation at any time or skip any part of the study if they are not comfortable.

A copy of the consent form is included in the submission.

## 6.7. Costs/Reimbursement

This study will be conducted online, so there will no costs incurred by subjects as a result of participation.

## 6.8. Compensation/Incentives

Study	Payment per participant	Payment schedule	Rationales
Screening survey	\$0.2	After study completed	\$12 per hour, as recommended by Prolific
Main experiment (completed)	\$3	After study completed	\$12 per hour, as recommended by Prolific
Main experiment partial payment	\$0.2	After participants return their submission	\$12 per hour, as recommended by Prolific
Follow-up survey	\$1	After study completed	\$12 per hour, as recommended by Prolific

*Note:* Prolific charges 25% of service fee for each study.

## 6.9. Withdrawal/Termination

Participants can choose to stop their participation at any time. Because this research project consists of three parts: the screening survey, the main experiment, and the follow-up survey. In the event participants withdrawal after completing one part, their data for the completed part will be kept. For example, a participant completes the main experiment but not the follow-up survey, their data in the main experiment will be kept.

Note that Sticky by Tobii (the webcam-based eye-tracking) will report a "terminated" category from those that begin the eye-tracking portion of the study. These include participants that terminate their participation voluntarily (e.g., close the browser) and encounter technical failures (e.g., cannot calibrate). If a participant is terminated by the eye-tracking platform, they will not be allowed to complete the rest of the study because

the remaining questions depend on the stimuli embedded in the eye-tracking task. Thus, the terminated participants will be requested to return their submissions. In this case, their data will be removed. Given that participants will answer a few questions before they are directed to the webcam-based eye-tracking platform, partial payments will be made to those who encounter technical failures but not those who withdraw from the study.

## 7. Study Procedures

Given that this project consists of three parts: the screening survey, the main experiment, and the follow-up survey; below is a description of each part. No personally identifying information will be collected throughout the entire project. Only participants' Prolific IDs will be used to connect data across the three parts.

**The screening survey:** Potential participants from the Prolific will first be invited to participate in a short online screening survey. The screener will be built using the Qualtrics survey platform. We will prescreen the sample to some extent using the Prolific' existing prescreening options, including currently residing in the U.S., being at least 21 years old, drinking at least one unit of alcohol on average per week, and having webcam or built-in camera that they are willing to use as part of a study. The screening survey will include five questions related to their age, average weekly alcohol consumption, and technical support to complete eye tracking tasks. Participants must meet the following inclusion criterion to be invited to participate in the main experiment: 1) be at least 21 years old; (2) have consumed more than three alcoholic drinks per week over the past year; and (3) be willing to participate in remote eye tracking tasks and have necessary technical support and physical environment to complete remote eye tracking tasks. The entire duration of the screening survey is expected to be about 1 minute.

**The main experiment:** Eligible participants will be invited to participate in the main experiment through the Prolific site. Once they sign up for the main experiment, they will be redirected to the online experiment built in Qualtrics survey platform. Participants will be first asked to sign the consent form and provided details about the study purpose and procedure. They will be informed that they will need to turn on their cameras when completing the eye-tracking task. Although their faces and surroundings will be recorded during the remote eye-tracking task, the researchers will not have access to these recordings. Consented participants will first answer several questions designed to measure baseline tobacco and alcohol consumption, alcohol-related knowledge, and the device they are currently using to be directed to the corresponding mobile or desktop-based eye-tracking experiment. Next, participants will engage with a webcam-based eye-tracking task. They will first read instructions and tips related to completing the eye-tracking task. They will then go through a calibration procedure to ensure good tracking. Participants will then be randomly assigned to view an order-randomized stimulus set containing either three narrative PWLs or three non-narrative PWLs. Narrative PWLs will contain photos of cancer

patients, and non-narrative PWLs will include images of diseased organs. All PWLs will include a simple, clear warning statement (e.g., “WARNING: Drinking alcohol can cause oral cancer.”) to describe the specific cancer risk associated with alcohol. Within each warning type, one will focus on oral cancer, one on esophageal cancer, and one on larynx cancer. All three cancers have higher relative risks for moderate and heavy drinkers compared to other types of cancer linked to alcohol. Participants will be instructed that the image will be displayed for 20 seconds and that they need to stay as still as possible while viewing. After viewing each PWL, they will proceed to answer questions designed to measure perceived attention, reactance, and narrative construction within the eye-tracking platform. After viewing all three PWLs, participants will answer additional questions about their and affective and cognitive responses toward the warnings, alcohol-related cancer risk perceptions and behavioral intentions, and policy support for the warnings. They will then answer a few questions designed to collect socio-demographic information at the end of the study. Upon completion of the study, participants will be debriefed. They will be reminded that they will be invited to participate in a follow-up survey in two weeks. The entire duration of the main experiment is expected to be about 15 minutes, with 5 minutes spent on completing the eye-tracking portion and 10 minutes on answering questions via the Qualtrics survey platform.

**The follow-up survey:** Participants who completed the main experiment will be invited to participate in the follow-up survey after two weeks. The follow-up survey will include questions about their behaviors related to drinking and the labels in the past two weeks. Risk perceptions, intentions, and policy support measured in the main experiment will be measured again to assess the long-term effect of narrative (vs. non-narrative) PWLs. The entire duration of the follow-up survey is expected to be about 5 minutes.

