## **5. Analytical Plan**

We will analyze the data using the statistical software SPSS. First, we will use descriptive statistics to provide study sample characteristics. Then, we will conduct independent-samples *t*-tests and chi-square tests to check whether there are differences in background variables (i.e., demographic characteristics and baseline alcohol consumption) between conditions. If there are a significant association between the experimental condition and a specific background variable(s), we will control for this variable(s) in all analyses. To test the first hypothesis, we will conduct multilevel mixed-effects linear regressions to examine the effect of narrative (vs. non-narrative) PWLs time until noticed, time viewed, and number of visits, and reactance. We will also control for repeated measures because each participant will view three PWLs that vary in cancer type within their assigned

condition. We will check the assumptions of these analyses. To test the second hypothesis, we will conduct independent-samples t-tests to examine the effect of PWLs type (narrative vs. non-narrative) on risk perceptions and behavioral intentions when there are no differences in the distribution of background variables between conditions. If there are differences in the distribution, we will conduct a series of analyses of covariance (ANCOVA). Assumptions of these analyses will be checked.

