response to each PWL, affective and cognitive responses after viewing all PWLs, risk perceptions, intentions to reduce and stop drinking, and policy support. The primary outcomes include attention, reactance, risk perceptions, and intentions, as stated in the hypotheses. The secondary outcomes include avoidance, narrative construction, affective and cognitive responses (i.e., processing fluency, affect, cognitive elaboration, and retrospective reflection), attitudes toward alcohol, intentions to forgo alcohol, intentions to avoid the warnings, and policy support for the warnings. The secondary outcomes are measured to explore the underlying psychological mechanisms of narrative (vs. non-narrative) PWLs. See the attached questionnaire for the self-report questions. Here, we describe how attention will be measured with the eye-tracker. Specifically, attention to each PWL will be measured with three eye tracking statistics: time until noticed, time viewed, and number of visits. Three areas of interest (AOI) will be defined a priori for each PWL, including (1) warning image, (2) warning text, and (3) entire warning label. All AOIs are consistent in size and location on each stimulus. Time until noticed measures the time between stimulus onset and the arrival of the participant's gaze into a specific AOI, which often reflects an AOI's ability to grab visual attention relative to other elements of a stimulus. Time viewed measures the average amount of time spent on an AOI, and it signals attention and cognitive processing. Number of visits measures the total number of unique times the AOI was viewed, which is an indicator of interest. Finally, socio-demographics will include questions related to their age, biological sex, gender identity, ethnicity, race, education, household income, political ideology, medical statistics literacy, and cancer history.

**The follow-up survey:** The follow-up survey will include questions related to their behaviors in the past two weeks, including drinking behavior change due to the labels, information seeking behaviors, and social interactions. Risk perceptions, attitudes, intentions, and policy support assessed in the main experiment will be measured again in the follow-up survey.

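### Device version (mobile or desktop) is recorded before randomisation but cannot enter the H1 gaze models; adding it as a fixed effect is a nearly free gain in precision

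*Combined protocol and SAP*

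**What the plan says.** Eligibility (section 6.1, repeated in 6.3) allows several kinds of device: "having access to high-speed Internet and a computer/tablet/phone equipped with a high-speed camera". In section 7 (main experiment), the questions before exposure include "the device they are currently using to be directed to the corresponding mobile or desktop-based eye-tracking experiment". Calibration follows, and then: "Participants will then be randomly assigned to view an order-randomized stimulus set containing either three narrative PWLs or three non-narrative PWLs". No section says that this assignment is stratified or balanced by device.

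For H1, section 5 specifies multilevel mixed-effects linear regressions "to examine the effect of narrative (vs. non-narrative) PWLs time until noticed, time viewed, and number of visits, and reactance". The only other term it names is for the repeated viewing: "We will also control for repeated measures because each participant will view three PWLs that vary in cancer type". A covariate is added only if a test finds "differences in background variables (i.e., demographic characteristics and baseline alcohol consumption) between conditions". Device is not in that definition, nor in the socio-demographic list in section 7.1. No section adjusts for device or plans an analysis by device.

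Section 7.1 says of the areas of interest: "All AOIs are consistent in size and location on each stimulus". That describes the layout of a stimulus. It does not say how a phone display compares with a desktop display.

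**The concern.** The device decides which version of the eye-tracking experiment produces a participant's gaze data. Display size and camera could plausibly shift the mean of all three gaze measures, although the documents report no such difference. A variable of this kind, known before assignment, would normally be in the model. Here it is collected and then has no route into the analysis: the covariate rule would exclude it even if the arms were badly unbalanced on device.

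Device is constant within a participant. In a mixed model with a participant-level random effect, an omitted device difference therefore adds to the between-participant variance and not to the within-participant residual. Condition is also assigned between participants, so this is the variance against which the condition effect is tested. What is at stake is the width of the intervals and the power for visual attention, a primary outcome under H1.

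**Working it through.** **Inputs from the documents.** Section 6.2.1 gives r = .19 (from preliminary work on reactance), alpha .05, power .80, N = 213, 43% usable eye-tracking data and 800 to be enrolled. Its earlier target gives 500 × .43 = 215 usable, so 213 is a number to be analysed. Section 11.2 keeps 213 as the floor for continuing recruitment, counted there as completers. With 800 enrolled, 800 × .43 = 344 usable records.

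**Reproducing the plan's figure.** d = 2r/√(1 − r²) = .38/√.9639 = .387. For two-sided alpha .05, 80% power and equal arms, the normal approximation gives 105 per arm (N = 210), the exact t-test gives 211.5 (N = 212), and Fisher's z gives 215.2 (N = 216). The stated 213 lies among these and is reproduced. A one-sided Fisher z calculation gives 171 and does not reproduce it. Power at 213 is .803; at 344 it is .947.

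**Effect of leaving device out.** Let p be the mobile share and D the mean mobile–desktop difference, in within-device SDs of the participant mean. Omitting device multiplies the participant-level variance by 1 + p(1 − p)D², and the standardised effect becomes .387/√(1 + p(1 − p)D²).

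The documents give neither p nor D. Assumed: p from .1 to .5, D from 0.25 to 1.0, 1:1 allocation, and .387 as the within-device effect on gaze. For example, p = .5 and D = 1.0 give 1 + .25 × 1 = 1.25 and .387/√1.25 = .346.

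| p | D | Variance factor | d without device | Power, 213 | N for 80% | Power, 344 |
|---|---|---|---|---|---|---|
| .1 | 0.25 | 1.006 | .386 | .80 | 214 | .946 |
| .3 | 0.5 | 1.052 | .377 | .78 | 224 | .937 |
| .5 | 0.8 | 1.160 | .359 | .74 | 246 | .914 |
| .5 | 1.0 | 1.250 | .346 | .71 | 264 | .893 |

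The first and last rows are the extremes of the assumed range. With device in the model, power is .80 at 213 and .947 at 344.

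**If .387 already includes device variance.** Modelling device then raises power at 213 from .803 to between .805 and .882 over the same range. The direction is the same.

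**Simulation.** Participant means, N = 213, 6,000 runs per setting:
- p = .5, D = 1.0: power .705 without device and .797 with it; type I error .053 both ways.
- p = .3, D = .5: power .786 without device and .804 with it; type I error .054 and .050.

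**The case against.** The strongest reply is that an unadjusted randomised comparison is valid. Assignment comes after device routing, so device is balanced in expectation, and the simulated type I error stays near .05 with or without it. That stands. A reader might infer that pooling the two versions biases the gaze comparison; nothing in the documents supports this. Nor is chance imbalance on device a second harm beside the larger standard error: over repeated randomisations it is already part of the unadjusted standard error.

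A reader might also infer that two instruments with different scales are being pooled. The documents describe one vendor platform and the same three statistics, and report no device difference in scale, tracking quality or area-of-interest behaviour. If scales did differ, one additive term would not repair it. The case made here needs only a possible difference in means.

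Third, H1 is not left underpowered by the plan's own standard if 344 usable records are reached: power stays at or above about .89 throughout the assumed range. This also stands, with two reservations. The .387 comes from reactance, and section 6.2.1 says no published work has examined the effect on visual attention. And 213 remains the floor in section 11.2, where there is no slack.

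Finally, H1 makes no claim about device, and within-device results would be weak. With a 30/70 split of 344 (about 103 and 241), the mobile group alone has 80% power only for d of about 2.802 × √(4/103) = .55. The interaction would need a difference in effects of about 2.802 × √(4/103 + 4/241) = .66.

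**Conclusion.** The omission is certain from the text: device is known before randomisation, is in no model, and cannot enter under the stated rule. Its consequence is a loss of precision for the three gaze outcomes, of a size the documents do not fix. Under the assumed ranges the loss runs from negligible (variance up 0.6%) to moderate (up 25%). With 344 usable records it leaves H1 comfortably powered at d = .387; with only 213, power could fall to about .71. These figures assume that the reactance effect carries over to gaze and that 43% of the 800 enrolled give usable data. The point is therefore a low-cost improvement to the analysis. It is not a threat to the validity of H1.

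**What to change.** Add one sentence to section 5: device version (mobile or desktop, as recorded before assignment) is a fixed effect in the models for time until noticed, time viewed and number of visits, whatever the balance tests show. It is a legitimate baseline covariate because condition cannot affect it.

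The cost is one degree of freedom per model and no new data. Since section 6.2.1 reports 404 participants already completed, the change should be dated before gaze data are examined by condition. Within-device estimates and the condition-by-device interaction are optional. If reported, they should be labelled descriptive because they would be imprecise.
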